2.2 Immune/inflammatory signaling-target gene expression pathways (secondary variables): Whole blood/CSF will be collected using PAXgene® Blood RNA Tubes (Qiagen) shipped to the centers. Blood from healthy subjects and CSF from patients with normal pressure hydrocephalus will serve as controls. Total RNA will be extracted using PAXgene® Blood RNA Kit (Qiagen). RNA samples are quantified using Qubit 2.0 Fluorometer (Life Technologies) and RNA integrity is determined with Agilent 2100 Bioanalyzer (Agilent Technologies). Expression levels of 44 genes related to immune/inflammatory (or cytokine) pathways (Table 2) will be measured with the nCounter® Digital Analyzer (NanoString). The raw copy number of mRNA transcripts of each gene will be standardized (stdGene) using the geometric mean of the 4 housekeeping genes for each subject. Then, a Z score for each gene will be calculated using the mean and the standard deviation (SD) of a group of 30 healthy subjects: Z score Gene = stdGene - mean stdGene control group/SD stdGene control group. A signature for each immune/inflammatory pathway in each subject will be calculated using the median of the Z scores of the genes involved in that pathway. The signature will be considered positive (e.g., activated) if the value is ≥ 1.96 (>98centile) (one tail analysis is used since only positive signatures are expected). We reported similar methods for the interferon pathway in another disorder.[27] It will include genes of B cell activation/function (CCL19, CxCL13, BAFF, APRIL, SYK, TACI, BAFFR, BCMA, CD40), T ell activation/function (CLDN1, IL23A, CTLA4, ICOS, ICOSLG, PDCD1, PDCD1LG2, CD40LG), TH17 signaling (IL17A, IL17RA), IL1 signaling (IL1RN, IL1B, IL1R1), IL2 signaling (IL21, IL21R), IL6 signaling (IL6, IL6R), other cytokine signaling (CXCL3, CXCL8, CX3CL1, IL12B, TNFAIP3), type 1 interferon signaling (IFI27, IFI44, IFI44L, ISG15, RSAD2, SIGLEC1), housekeeping genes (ALAS1, HPRT1, TBP, TUBB).

2.3 Neurofilament light chain (NfL) levels (secondary variables): will be determined in serum and CSF using the SiMoA Quanterix technique. These studies will provide a signature of molecular biomarkers in the acute and post-acute stages. We expect they will correlate with symptoms and psychophysical biomarkers (Aim1) and will assist in treatment decisions.

3. Determine in an animal model the pathogenic mechanisms and treatment of the post-acute stage of NMDARe.

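### Gene-expression signatures use untransformed Z scores with a normal-theory cut-off, so the false-positive rate varies by pathway and is not the stated under 2%

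*Protocol*

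**What the plan says.** Section 4.1, item 2.2 sets out the rule in full.

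- Counts are normalised first: "The raw copy number of mRNA transcripts of each gene will be standardized" with the geometric mean of the four housekeeping genes.
- Then "a Z score for each gene will be calculated using the mean and the standard deviation (SD) of a group of 30 healthy subjects". The printed formula is "Z score Gene = stdGene - mean stdGene control group/SD stdGene control group", which makes sense only with brackets around the difference. It works directly on the normalised count, and no transformation is mentioned.
- Each subject's pathway score is the median Z over that pathway's genes.
- The call is made on that median: "The signature will be considered positive (e.g., activated) if the value is ≥ 1.96 (>98centile"). The reason given for using one tail is that "one tail analysis is used since only positive signatures are expected".

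The gene lists in the same item give pathway sizes of 9 (B cell), 8 (T cell), 6 (type 1 interferon), 5 (other cytokines), 3 (IL1) and 2 (TH17, IL2 and IL6). The item is a secondary variable.

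**The concern.** A limit of mean plus 1.96 SD corresponds to a known centile only for a roughly normal quantity. A housekeeping-normalised count is positive and usually multiplicative in behaviour. The plan itself treats the housekeeping genes that way by using a geometric mean, then returns to the arithmetic scale for the mean and SD. On that scale a right-skewed gene has a heavier upper tail than the label implies, and the SD from 30 controls depends strongly on the few largest values.

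The score that is classified is a median of 2 to 9 such Z scores. Taking a median narrows the spread unless the genes move together, which pulls the rate down. The two effects oppose each other and differ in strength between pathways, so a positive signature does not mean the same thing in TH17 as in the B-cell set.

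The stake is interpretation. Objective 2 uses the acute versus post-acute comparison when assessing the need for immunotherapy, and item 2.3 expects the biomarkers to assist treatment decisions. Pathways with unequal false-positive rates cannot be compared fairly for either purpose.

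**Working it through.** **Inputs from the protocol.** 30 controls; cut-off 1.96, one tail; median of k gene Z scores; k = 2, 3, 5, 6, 8 or 9.

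**Assumptions.** The protocol gives no distribution, skew or correlation. Expression is taken as log-normal with log-SD σ, and genes within a pathway share a correlation ρ on the log scale.

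**Step 1: the plan's own figure.** For one normal Z score with known mean and SD, Φ(1.96) = 0.975. That is the 97.5th centile and a one-tailed rate of 2.5%. The 98th centile is 2.054. The label holds only by rounding 97.5 up.

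**Step 2: one gene, known mean and SD, raw scale.** For a log-normal with log-mean 0, the mean is exp(σ²/2) and the SD is √[(exp(σ²) − 1)·exp(σ²)]. The rate is 1 − Φ[ln(mean + 1.96·SD)/σ].
- σ = 0.5: 4.6%.
- σ = 1.0: mean 1.649, SD 2.161, limit 1.649 + 1.96 × 2.161 = 5.885, ln = 1.772, rate 3.8%.

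**Step 3: one gene, mean and SD estimated from 30 controls.** On the log scale the rate is P[t₂₉ ≥ 1.96/√(1 + 1/30)] = P[t₂₉ ≥ 1.928] = 3.2%. On the raw scale, simulation gives 5.0% to 6.4% for σ from 0.25 to 1.0. No signature in the plan is a single gene, so this step shows only the size of the skew effect.

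**Step 4: the signature itself.** Simulation used 40,000 control sets of 30, with five new healthy subjects each. The table gives the percentage with median Z ≥ 1.96. Raw-scale ranges cover σ from 0.25 to 1.0.

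| Genes | ρ = 0.3 raw / log | ρ = 0.5 raw / log | ρ = 0.7 raw / log |
|---|---|---|---|
| 2 | 2.4–5.1 / 1.1 | 3.2–5.5 / 1.7 | 3.9–6.0 / 2.3 |
| 3 | 1.7–2.5 / 0.9 | 2.5–3.5 / 1.4 | 3.5–4.6 / 2.1 |
| 5 | 0.9–1.4 / 0.4 | 1.9–2.7 / 1.0 | 3.0–4.1 / 1.8 |
| 6 | 0.7–1.2 / 0.3 | 1.7–2.5 / 0.8 | 3.0–3.9 / 1.7 |
| 8 | 0.5–0.8 / 0.2 | 1.5–2.2 / 0.7 | 2.8–3.8 / 1.6 |
| 9 | 0.5–0.8 / 0.2 | 1.5–2.1 / 0.7 | 2.8–3.7 / 1.6 |

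Starting at σ = 0.3 raises the lowest two-gene figure to about 2.6% and leaves the upper ends unchanged. On the raw scale the rate moves with σ, ρ and k. On the log scale it does not depend on σ, but it still depends on ρ and k.

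**Step 5: re-standardise the signature.** Subtract the controls' mean signature, divide by the SD of their signatures, and apply 2.054.
- Raw-scale Z scores: about 4.0% to 6.8%.
- Log-scale Z scores: about 2.5% to 2.9% for every pathway size, σ and ρ tried.

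The remaining excess over 2% comes from estimating the mean and SD from 30 controls: P[t₂₉ ≥ 2.054/√(1 + 1/30)] = P[t₂₉ ≥ 2.021] = 2.6%.

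**The case against.** **Over-calling is not general.** A reader might infer that the raw scale makes signatures positive too often across the board. The document does not support that. At correlation 0.3 every pathway of five or more genes falls below 2% even on the raw scale, and at 0.5 the 6- to 9-gene pathways are close to nominal. The protocol gives neither skew nor correlation, so the direction for the larger pathways is unknown. This objection stands, and the point is limited accordingly.

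**Logging alone does not repair the rule.** This also stands. With 1.96 kept on the median, log values leave the 6- to 9-gene pathways at 0.2% to 0.8% for correlations of 0.3 to 0.5, further from 2% than the raw scale in several settings. The cut-off has to move to the signature's own scale as well.

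**The log step might then seem redundant, since re-calibrating against controls could suffice.** Step 5 answers this: mean-and-SD re-standardisation on the raw scale still gives about 4.0% to 6.8%.

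**A transformation may belong in the analysis plan or in the cited interferon method, neither of which is at hand.** This stands in part. But the protocol fixes the scale, formula, statistic and cut-off together, so it states a rule and does not merely leave a detail open. The precedent it cites is for interferon, here a six-gene set, and is not evidence for two-gene sets.

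**A positive signature might be read as triggering treatment.** No section ties an action to crossing 1.96. The wording on treatment is an expectation.

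**Conclusion.** The concern holds in a limited form. The rule applies a normal-theory limit to untransformed ratios, and the stated rate of under 2% is not what it delivers if expression is right-skewed. Under log-normal expression with log-SD 0.3 to 1.0, correlation 0.3 to 0.7 and 30 controls, the two-gene pathways are over-called at about 2.6% to 6.0%. The 6- to 9-gene pathways range from about 0.5% to about 4%. What can be said of all pathways is that the error rate is uncontrolled and differs between them, not that it is always too high. Log-normality, the log-SD and the correlation are assumptions, and the size of the problem changes with them. Separately, 1.96 is the 97.5th centile and not above the 98th, a small labelling error. Because the variable is secondary and no decision rule hangs on the cut-off, this is a worthwhile improvement and not a serious flaw.

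**What to change.** In item 2.2:

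1. State that housekeeping-normalised values are log2-transformed in patients and controls before the mean, SD and Z are computed, with a fixed offset for zero counts. Put the missing brackets in the Z formula.
2. Keep the median of the gene Z scores, then re-standardise it by the mean and SD of that same median in the 30 controls.
3. Apply the cut-off to the re-standardised signature: 2.05 for the 98th centile, or 1.96 relabelled as the 97.5th. State that, with 30 controls, the actual rates run somewhat above nominal (about 2.5% to 2.9% for 2.05).
4. Check the distribution of the logged values in the controls, since the gain depends on logging removing most of the skew.
5. Report the raw-scale version once as a sensitivity analysis.

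The cost is a few lines of code and no change to sampling, visits or assay. There will generally be fewer positives in the two-gene pathways, and there may be more in large pathways whose genes are weakly correlated. Direct comparability with the group's earlier interferon method is reduced, which the sensitivity analysis partly restores.

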a) Characterizing the post-acute stage. There is very limited knowledge of the post-acute stage of NMDARe; it is even unclear if immunotherapy or only symptomatic treatment is needed (antibody titers are not useful for these decisions). In a pilot prospective study we found an array of previously under-recognized symptoms (sleep and psychiatric alterations, inappropriate behavior, memory and cognitive deficits) [9]. Some patients were re-admitted to psychiatric facilities and we are aware of patients prosecuted for inappropriate social behavior. In this study, which also included a group of persons with schizophrenia (SCZ) and a group of healthy participants, we found that the cognitive and psychiatric symptoms of the post-acute stage of NMDARe resembled those of patients with stabilized SCZ. Despite sustained improvement in psychiatric scales, longitudinal follow-up showed that the cognitive deficits of NMDARe, but not those of SCZ, improved initially but stagnated at ~6 months. This represents an opportunity for targeted treatment that we will address in this proposal. The mechanisms underlying these alterations are unknown. Psychophysical testing showed that patients with NMDARe or SCZ had intact precision in a working memory (WM) task but a strong reduction of serial dependence (which is the influence of previous experiences in performing the WM task [17]). In animal models serial dependence of similar WM task relates to synaptic plasticity [18], suggesting a role for NMDAR-dependent short-term synaptic potentiation in NMDARe.[17] In longitudinal studies, the WM alteration of serial dependence along with other symptoms improved gradually in NMDARe towards the value of healthy controls. Additionally, in the same pilot study, we identified that patients with NMDARe had changes in the slope of individual slow-waves during deep sleep (postulated to reflect synaptic strength).

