- 3.1 Memory and behavioral tests for mice (primary variables)
- 3.2 Surface clusters of NMDARs on sections of cortex/hippocampus (primary variables)
- 3.3 Hippocampal long-term (LTP) and short-term potentiation (STP) (secondary variables)

3.4 Immune/inflammatory signaling-target gene expression pathways (secondary variables): will include genes of B cell activation/function (CCL19, CxCL13, BAFF, APRIL, SYK, TACI, BAFFR, BCMA, CD40), T ell activation/function (CLDN1, IL23A, CTLA4, ICOS, ICOSLG, PDCD1, PDCD1LG2, CD40LG), TH17 signaling (IL17A, IL17RA), IL1 signaling (IL1RN, IL1B, IL1R1), IL2 signaling (IL21, IL21R), IL6 signaling (IL6, IL6R), other cytokine signaling (CXCL3, CXCL8, CX3CL1, IL12B, TNFAIP3), type 1 interferon signaling (IFI27, IFI44, IFI44L, ISG15, RSAD2, SIGLEC1), housekeeping genes (ALAS1, HPRT1, TBP, TUBB).

5 Design of the study

Human studies

This is a prospective single center, single arm, national study of 3 years duration.

The study will be conducted following the protocol that we developed for a previous prospective longitudinal observational study that was performed between 2017 and 2021 with patients with anti-NMDAR encephalitis during the post-acute stage, and that was approved by the CEIm of HCB (Study title: "Immune-mediated diseases of the synapse: symptoms, brain networks, and the link to human memory"; PI: [name]; Code: HCB/2016/0596). We will perform the exact same protocol with 3 main novelties: (1) we include five remote online study visits (clinical assessments and tasks using portable devices); (2) patients will undergo a cognitive rehabilitation program, and (3) they will have two CSF studies, as detailed below.

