20 newly diagnosed NMDARe patients (age ≥12 years) will be recruited. Families and patients will be approached during the acute phase of the disease and invited to participate in the study after hospital discharge. Informed consent and general clinical information through a structured questionnaire will be obtained from participants/legal guardians. Identification of patients will be done in (1) our hospitals, (2) through a network of Spanish hospitals, both adults and pediatrics (already in place, specified in the Annex), and (3) the Neuroimmunology lab at HCB/IDIBAPS (referral center for NMDARe). Because NMDARe predominates in women (8:2), it is expected that there will be a female predominance.

Inclusion criteria

Patients \geq 12 years old with NMDARe in the post-acute stage of the disease, \leq 6 months from hospital discharge (acute phase), will be eligible to participate in the study.

Exclusion criteria

They include: inability to obtain informed consent or inability to travel to our center.

External control group

Patients from a pilot study (n=20; follow-up \geq 2 years; HCB/2016/0596) who underwent similar presential visits (without cognitive rehabilitation or remote assessments/tests) will be contacted to extend their follow-up for an additional year. For patients followed up at our institution, we will take advantage of a regular follow-up visit to inform them about the study and obtain their consent. For patients cared for at other hospitals, the referring doctors will explain the possibility of participating in the current study and, if the patients consent, we will contact them to provide further explanations and in such case obtain the informed consent. They will have 2 additional presential visits (as above) 1 year apart, and blood tests. This group will serve as control and will be compared with newly recruited patients (with cognitive rehabilitation/remote tests). They will provide a long-term followup (\geq 3 years) without remote cognitive rehabilitation or tests and will help to assess the impact of these interventions in outcome, and whether immunologic/ inflammatory signatures or signs of neuronal injury (NfL) are chronically present in blood.

7. Treatment and calendar of the study

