The general outline of the study including presential and remote visits and cognitive training is summarized in **Figure 1**; and the evaluations and tests during each of the three presential visits (except CSF studies that will be performed only in the first and last visit) are shown in **Figure 2**. A more detailed description of tests, interventions and calendar of the studies is provided following both figures.

Figure 1: Outline of presential and remote visits and cognitive training

V1, V2, V3= visitas presenciales; V1= 1st visita de estudio; V2= seguimiento a los 6 meses; V3= seguimiento al 1 año
A→D= entrenamiento cognitivo; A,B= 2 sesiones/semana; C= 1 sesión/semana; D= 1 sesión/2 semanas
R₁, R₄, R₅ = evaluación cognitiva remota (estudio comparativo con V1, V2 y validación de estudio remoto)
R₂, R₃, R₅ = evaluación psiquiátrica remota R₂, R₃= dispositivos portátiles (Memoria, EEG/sueño); s= semanas

Figure 2. Schedule for each presential visit

Presential visits

This study includes a total of 3 presential visits during 1 year. After hospital discharge, patients will come to our center ~2-5 months after disease onset for the **first (baseline) presential study visit (V1)** and for **follow-up visits 6 months (V2)** and **12 months (V3)** after V1. Each visit will consist of 2 days and 1 night admission at HCB (children, adults) during which they will undergo clinical examinations and tests according to a pilot study, including: neuropsychiatric and cognitive assessments, psychophysical studies, MRI, v-PSG, EEG. At V1 and V3, patients will undergo blood and CSF studies (variables 2.1, 2.2 and 2.3 will be analyzed in these paired blood/CSF samples and will be compared with those from the acute stage).

- Presential standard neuropsychiatric examinations and cognitive assessments will be conducted as per routine clinical practice and with a reported panel of neurological functional, cognitive and psychiatric tests (variables 1.1, 1.2 and 1.3). Total time ~4h spread over 3 sessions (the exact timetable can be adapted to patients' preferences and the length of the interviews will vary according to patients' clinical status; the times are indicative and are overestimated to be sure). These clinical evaluations will take place in the same room where the patients will sleep, and patients will have enough pauses in between to rest, eat/drink and go for a walk outside the hospital with their relatives.

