Remote cognitive rehabilitation program will be performed through an online validated platform (Guttmann Neuropersonal Trainer [GNPT]: https://gnpt.es/) run by our team. This is a Sanitary Product with CE certification (Producto Sanitario RPS/430/2014; International Patent [PCT/ES2008/00677]) and here will be used within its approved indications. The rehabilitation program will increase in difficulty and decrease in frequency during the first year of follow-up (V1-V3).

Patients/families will be instructed to perform remote cognitive rehabilitation during the presential visits. Patients will be able to use their personal computer and access via an available link and a user code the GNPT platform. In case that they do not have easy access to adequate equipment to access the platform, we will provide the iPad tablet with all the necessary software installed and ready to use to support their training. The indicated frequency of cognitive training is based on results of a recently published pilot study in which patients were followed with only presential visits (no remote visits or cognitive training was provided). The study showed that a slow progressive cognitive improvement occurred in most patients during the 1 year follow-up. However, the improvement was more marked during the first 6 months compared with the last 6 months. This finding suggested that intensive cognitive training (particularly during the first 6 months) could

accelerate recovery and improve outcome. Accordingly, for the current study patients will undergo cognitive rehabilitation twice per week for the first 6 months and once per week for the last 6 months. Similar programs are currently used by our team for patients with multiple sclerosis (along with collaborations with Institute Guttmann, Barcelona). Remote cognitive sessions will take ~45-60min.

Experimental mouse model of NMDARe

These studies are separate from the human studies. The animal study protocol is currently under revision by the CEEA-UB with registration number 420.22, already pre-approved. As indicated, no human biological samples will be used for the experimental animal model. Of note, although the animal studies are independent of human studies, the running in parallel of both sets of investigations will inform on the mechanisms of the disease and may have future treatment and prognostic implications.

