8.2. Statistical analyses

For human studies, we will analyze differences in cognitive and psychiatric variables between and within groups (newly recruited NMDARe patients and those from the pilot study) in the longitudinal follow-up using multilevel linear mixed-effect models, adjusting for group, age, sex, and socioeconomic status to control for possible confounds. Lme4 R package will be used to fit LME models, and residual plots will be used to validate them. Comparisons will be done with emmeans library and Tukey method for post-hoc correction for multiple testing. The global tendency of recovery of cognitive deficits in NMDARe (proportion of patients compared to the general population in each domain) will be assessed with the Cochran-Armitage test for trend; other comparisons within NMDARe will be done with Wilcoxon signed-rank and McNemar's tests. The patient behavioral, PSG and EEG data will be analyzed with linear regression using multiple regressors (task parameters, fraction of NREM N3, disease condition, with/without remote training, etc.). All analyses will be addressed considering a two-tailed type I error of 5% with statistical significance set at p-value <0.05, using SPSS (IBM Corp, Armonk, NY) and R package (Vienna).

For animal behavior studies with multiple determinations in time (e.g., new object recognition) we will use the double variance analysis (ANOVA). For behavior studies with a single determination in time (e.g., depressive behavior; "tail suspension") we will use the simple ANOVA. Electrophysiological studies (long-term potentiation) will be analyzed with double ANOVA. In all experiments, the post-hoc analysis will use the Bonferroni correction for multiple tests. A value of p <0.05 will be considered significant. The alpha-error will be set to 0.05. The analyses will be done using GraphPad Prism. Animal sample size: To detect a difference between the two groups with a 95% CI, assuming an estimated standard deviation of 20% for behavioral tests and a 20% procedural mortality, we will need 12 mice per group.

9. Risks and benefits for participants in the study

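### Eligibility is counted from discharge and V1 from onset, and the stated adjustment set leaves out onset-to-V1 time, a potential confounder of the comparison with the pilot cohort

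*Protocol*

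**What the plan says.** Four parts of the protocol bear on this point.

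- **Entry.** Section 6 (Inclusion criteria) sets an upper limit counted from discharge: patients at most "6 months from hospital discharge (acute phase), will be eligible to participate in the study". It sets no limit on time since onset.
- **Baseline.** Section 7 (Presential visits) counts from onset: after discharge, "patients will come to our center ~2-5 months after disease onset" for V1. V2 and V3 follow 6 and 12 months after V1.
- **Course of recovery.** Section 2, item a), reports from the pilot study that cognitive deficits "improved initially but stagnated at ~6 months". Section 7 (Remote cognitive rehabilitation program) says of the same untrained patients that "the improvement was more marked during the first 6 months compared with the last 6 months".
- **Comparison.** Section 6 (External control group) says of the 20 pilot patients: "This group will serve as control and will be compared with newly recruited patients". Section 8.2 describes the mixed models as "adjusting for group, age, sex, and socioeconomic status to control for possible confounds". Time since onset or discharge is not in that list. Section 4.1, item 1.1, does collect the duration of symptoms.

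On how alike the cohorts are, section 5 says "We will perform the exact same protocol with 3 main novelties", and none of the three novelties concerns entry timing. The pilot's entry window and its actual V1 timing are not given.

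**The concern.** Two rules fix when a patient starts, on two different clocks, and nothing says which prevails when they part. This matters because the outcome of interest is change from V1 in a disease that improves without training, faster at first and more slowly later. A patient whose V1 comes early has more natural improvement still ahead than one whose V1 comes late.

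The control group is external and was recruited earlier, so randomisation does not balance the start point. If the new patients have their V1 earlier after onset than the pilot patients did, their larger natural gain would be credited to rehabilitation. If they have it later, a real benefit could be hidden. The covariates named in section 8.2 would remove neither distortion.

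**Working it through.** Section 8.1 sets 20 new and 20 pilot patients on feasibility and gives no power calculation for the human study, so there is no figure to reproduce. The check is timing arithmetic followed by an illustration.

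**Inputs**

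- From section 6: entry at most 6 months after discharge.
- From section 7: V1 after discharge, about 2 to 5 months after onset; V2 six months after V1.
- Assumed: time from onset to discharge L = 0.5 to 3 months.
- Assumed: ratio r of the natural gain in one six-month period to that in the next = 1.5 to 4. The protocol says only that the first is larger.
- Assumed: difference s between cohorts in mean onset-to-V1 time = 1 to 3 months.

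**Step 1: where the rules agree.** Time since discharge at V1 is time since onset minus L. At the upper end of the V1 window this is 5 − L, which is below 6 for any L above 0. Every on-schedule patient therefore meets the inclusion rule.

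**Step 2: where they part.**

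| L (months) | Latest eligible entry after onset, 6 + L | Latest entry after discharge that keeps V1 within 5 months of onset, 5 − L |
|---|---|---|
| 0.5 | 6.5 | 4.5 |
| 1 | 7 | 4 |
| 2 | 8 | 3 |
| 3 | 9 | 2 |

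Counted from 2 months after onset, V1 can spread over 3 months on the schedule and over 4 + L = 4.5 to 7 months on the inclusion rule. On-schedule V2 falls at 2 + 6 = 8 to 5 + 6 = 11 months after onset. With L of 2 or 3, a patient at the inclusion limit would have V1 at 8 or 9 months, where on-schedule patients already have V2.

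**Step 3: natural gain by start point (illustration).** Let the remaining deficit decay as r^(−t/6), with t in months since onset. The gain from V1 to V3 is then proportional to r^(−t/6) × (1 − r^(−2)). Relative to V1 at 3.5 months, the middle of the window, it is r^(−(t − 3.5)/6).

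| V1 at | r = 1.5 | r = 2 | r = 3 | r = 4 |
|---|---|---|---|---|
| 2 months | 1.11 | 1.19 | 1.32 | 1.41 |
| 5 months | 0.90 | 0.84 | 0.76 | 0.71 |
| 8 months | 0.74 | 0.59 | 0.44 | 0.35 |

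On this curve the ratio of successive six-month gains is the same from any starting point, so r may be read over follow-up or from onset.

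**Step 4: difference between cohorts (illustration).** If one cohort's V1 times are the other's shifted later by s, its natural 12-month gain is smaller by 1 − r^(−s/6).

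| s (months) | r = 2 | r = 3 |
|---|---|---|
| 1 | 11% | 17% |
| 2 | 21% | 31% |
| 3 | 29% | 42% |

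At s = 0 the shift is zero, and a wide window adds only variance. Precision is already limited: for 20 against 20, unadjusted, the difference detectable with 80% power at two-sided 5% is (1.96 + 0.84) × √(2/20) ≈ 0.89 SD.

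**Step 5: what an added covariate would correct.** Let T be a patient's onset-to-V1 time. With a main effect only, the mean at visit j in group g is μ(g,j) + βT, and βT cancels from V2 − V1 and V3 − V1. With a visit-specific slope, the change contains (β₂ − β₁)T or (β₃ − β₁)T, which is the part that needs correcting. With three visits this takes one main effect and two interaction terms, so three parameters.

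**The case against.** The best defence is that the inclusion limit is only an outer bound and the V1 schedule is what will happen. Section 6 has families approached during the acute phase, which favours early entry, and Step 1 shows the schedule nested inside the limit. A reader might infer that the two windows cannot both hold. The documents do not support that: V1 is given as approximate, and the rules diverge only for late entrants. What remains is that such entrants are admitted and no rule says what happens to them.

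A reader might also infer that the comparison is biased. That is not supported either. Bias from this source needs onset-to-V1 time to differ between cohorts, and section 5 points to a shared schedule. Section 6, however, calls the pilot visits only similar and gives no pilot timing, so a difference is neither shown nor excluded.

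A third tempting reading is a plateau at six months from onset. Section 7 counts its two half-years over the pilot's one-year follow-up, and section 2 does not state the zero point of its six months. Slowing recovery is documented; where it slows on the onset clock is not.

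Finally, covariates and visit windows are often refined in an analysis plan, and one may exist. Section 8.2 nevertheless names a specific list, offered as control for confounding, so it is fair to say what that list omits.

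**Conclusion.** The point holds as an ambiguity and an unaddressed potential confounder, not as a demonstrated bias. Three things rest on the text alone: the two clocks, the lack of a rule for late entrants, and the absence of time since onset from the stated adjustment set in a non-randomised comparison of change.

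The size is unknown. The 6.5 to 9 months depends on the assumed time from onset to discharge. Every percentage depends on an assumed exponential curve, and the between-cohort figures also on an assumed difference in mean timing. None of them estimates what will happen in this study. The direction would follow the sign of the timing difference. The change is worth making because it is cheap and the protocol's own description of recovery makes start time an evident prognostic factor for change.

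**What to change.** 1. Reconcile sections 6 and 7 so that eligibility and V1 are counted from one anchor, and state what happens to a patient who meets one rule and not the other. The choice of window is the sponsor's.
2. Report the distribution of onset-to-V1 time in both cohorts.
3. In section 8.2, add onset-to-V1 time together with its interaction with visit, or use time since onset as the time axis in a form that allows recovery to slow. A main effect alone is not enough (Step 5).

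The cost is a text correction and a few degrees of freedom with 40 patients: three parameters for a linear term with three visits. Onset dates must be retrieved for the pilot patients at their first visit. Symptom duration under item 1.1 should allow this for new patients, but the protocol does not show that it was recorded as a date or held for the pilot. If the cohorts overlap little in onset-to-V1 time, the adjustment becomes extrapolation and should be reported as such.
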